### 6.8.3. Other Secondary Efficacy Analyses

The same statistical analyses described in Section 6.8.1 will be performed for the following efficacy/pharmacodynamic measurements.

1. Patient's symptom specific daily diary scores
2. Proportion of days which meets a threshold of response criteria (See section 6.1)
3. Physician's Global Assessment of Disease Activity scores
4. Barthel Index (for SAVI and AGS)
5. Classification of disease severity (for NNS)
6. Prednisone (or equivalent) dose of systemic corticosteroids
7. Laboratory testing (e.g. CRP, complete blood cell count, AST, ALT, gammaglutamyltransferase [GGT], creatine phosphokinase [CPK])
8. Biomarkers (IFN response gene score, IFN signature score\*, Cytokine panel (serum IP-10/CXCL10, etc))
9. Inflammatory marker (High sensitivity C-reactive protein (hsCRP))

\* interferon (IFN) signature score is a composite score using 6 genes of IFN response gene score. The following is a equation of the calculation of IFN signature score.

IFN signature = Median(-1.4680 + 1.1938\*DDX60, 5.8581+0.6907\*IFI44, 1.8415 + 0.8009\*LY6E, MX1, 2.2300 + 0.8037\*OAS3, 6.4731 + 0.7148\*USP18) – 13.5

Regarding proportion of days which meets a threshold of response criteria, the following criteria described in Table JAJE.4 will be used. Additional threshold may be added.

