3.2.2. Functional Data Supporting a Rationale to Block IFN Signaling

Empiric treatment with targeted agents to TNF, IL-1, and IL-6 have been unsuccessful in patients with CANDLE. To characterize the inflammatory pathway and to identify therapeutic targets, the cytokine profile, transcriptome, and signaling pathways in these patients has been assessed. Interestingly, interferon inducible protein 10/C-XC motif chemokine 10 (IP-10/CXCL10) serum levels, were on average over 77-fold higher than controls. Very high levels of IP-10/CXCL10 suggested excessive IFN responses in CANDLE patients. Since STAT-1 is a downstream mediator of IFN- α/β and γ signaling, STAT-1 phosphorylation in the monocytes in response to IFN- γ stimulation has been studied. Compared with monocytes from healthy controls and a patient with neonatal-onset multisystem inflammatory disease (an IL-1 mediated autoinflammatory syndrome), monocytes from CANDLE patients showed stronger STAT-1

phosphorylation in response to all IFN- γ - concentrations used for stimulation (from 0.1 to 100 IU).

To probe for further evidence of excessive IFN signaling in CANDLE patients *in vivo*, the transcriptome in whole-blood microarray analysis in 4 CANDLE patients and 4 age- and gender-matched healthy controls were compared. CANDLE patients had 507 genes (650 transcripts) that were more than 2-fold differentially expressed compared to healthy controls ($p<0.05$), 238 of which were upregulated. Differentially expressed genes (DEGs) were analyzed by the Ingenuity Pathway Analysis program to identify dysregulated canonical pathways, and the IFN pathway was the most differentially regulated in CANDLE patients ($p=4.73^{E-06}$). Of the 238 upregulated DEGs, 41 (17.2%) were IFN-induced. Of the DEGs on the IFN-induced gene list in Ingenuity Pathway Analysis, all were IFN- γ induced ($n = 42$, 100%) and 6 (14.2%) were also regulated by IFN- α/β . The genes were plotted on a color-coded heat map, and the patterns of increased and decreased DEGs were strikingly similar among CANDLE patients, regardless of the presence or absence of detectable PSMB8 mutations. IP-10/CXCL10, which is highly expressed in the patients' serum, was among the IFN-induced upregulated genes. The DEG list from patients with CANDLE was compared with IFN-regulated genes published in www.interferome.org, and 119 of the 507 DEGs were found to be IFN regulated.

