### 5.2. Determination of Sample Size

Because the medical conditions being treated in the study are very rare in Japan, it is anticipated that relatively few patients will be enrolled. Approximately 5 patients will be enrolled. The sponsor will try to enroll more than 1 patient per disease.

However, given the scarcity of patient population for each of these target diseases in Japan, it may be possible that the study is completed without enrolling any patient for a specific disease if no eligible patient could be found.

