#### **NNS/CANDLE, SAVI, AGS**

**Baseline of the baricitinib treatment period** which includes dose adjustment period, primary treatment period and maintenance treatment period will be defined as the last available value before the first dose of baricitinib. In most cases, this will be the measure recorded at Week 0 (Visit 6). Change from baseline will be calculated as the visit value of interest minus the baseline value.

**Endpoint of the baricitinib treatment period** will be the last non-missing postbaseline measurement during the baricitinib treatment period. Major interest is the endpoint of the primary treatment period. Any measurements collected after the first dose of baricitinib will be considered a postbaseline measurement.

**Baseline of the post follow-up period** is defined as the date of the final visit or early termination in the treatment period. **Endpoint of the post follow-up period** is Visit 801.

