## 6.8. Efficacy Analyses

### 6.8.1. Primary Outcome and Methodology

The primary objective is to determine if the administration of baricitinib to patients with NNS/CANDLE, SAVI, or AGS results in reduction in the patient's mean daily diary scores compared to baseline.

For change from baseline in patient's mean daily diary scores (defined in Section 6.9.1), descriptive statistics will be calculated by visit for NNS/CANDLE, SAVI, and AGS for baricitinib treatment period including dose adjustment period, primary treatment period and maintenance treatment period. Primary interest is to assess the mean change from baseline in patient's mean daily diary scores at Week 20 in NNS/CANDLE and Week32 in SAVI and AGS during primary treatment period, which is the primary endpoint of the study.

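### Cytokines and hsCRP are summarised as raw change within each disease, so with two or three patients the mean leans to the one with the highest level and gives no relative size

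*SAP*

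**What the plan says.** SAP 6.8.3 opens with "The same statistical analyses described in Section 6.8.1 will be performed for the following efficacy/pharmacodynamic measurements" and then gives nine items. Item 8 includes "Cytokine panel (serum IP-10/CXCL10, etc" and item 9 is "Inflammatory marker (High sensitivity C-reactive protein (hsCRP".

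The analysis borrowed from SAP 6.8.1 is a set of descriptive statistics by visit, separately for NNS/CANDLE, SAVI and AGS. Its focus is the mean: "Primary interest is to assess the mean change from baseline in" the diary score. SAP 6.1.1 fixes the scale: "Change from baseline will be calculated as the visit value of interest minus the baseline value". SAP 6.1 adds the SD, minimum, maximum, median and number of observations to each mean.

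Neither document gives a ratio, logarithm, geometric mean or percent change for cytokines or hsCRP. The SAP does use percent change elsewhere: for corticosteroid dose (6.7) and for the diary score in the by-visit listing (6.8.3).

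On numbers, SAP 5.2 says "Approximately 5 patients will be enrolled" and "The sponsor will try to enroll more than 1 patient per disease", and allows that a disease may have no patient. The objectives tables in both documents rank change in biomarkers and inflammatory markers as exploratory, although SAP 6.8.3 is headed as secondary efficacy.

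**The concern.** A raw difference suits the diary mean, which is bounded. It cannot exceed 4 for NNS/CANDLE and SAVI. For AGS the limit is 34/8 = 4.25. No patient can outweigh the others by much.

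Serum IP-10, other cytokines and hsCRP are concentrations with no upper bound. When raw differences are averaged, a halving from 8000 counts twenty times as much as a halving from 400. The exploratory objective asks whether baricitinib changes these markers. With two or three patients in a disease, the raw mean answers that mostly for one of them. A figure in absolute units also does not tell the reader whether the fall was a tenth or nine tenths of the starting level.

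**Working it through.** The documents state no power, SD or marker level for this study, so there is no figure of the plan to reproduce.

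**Inputs from the documents.** Change is visit minus baseline (SAP 6.1.1). Summaries are by visit and disease (SAP 6.8.1). About 5 patients are planned over three diseases (SAP 5.2), which I read as about 1 to 3 per disease.

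**Assumed inputs.** Log-normal baselines with geometric SD 2, 3 or 5 between patients; a true halving in every patient; log SD 0.5 for a patient's ratio to baseline.

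**Step 1: who carries the mean.** With change d = visit − baseline, the share of the largest patient is max|d| / Σ|d|. Simulated results, as ranges over geometric SD 2 to 5:

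| | n=2 | n=3 |
|---|---|---|
| Largest patient's share of total absolute change (median) | 71% to 84% | about 56% to 72% |
| Raw mean change zero or positive | 5% to 6% | 3% to 5% |
| Geometric mean ratio 1 or more | 2.5% | 0.8% |
| SD of relative change, raw scale | 0.23 to 0.26 | 0.20 to 0.23 |
| SD of relative change, ratio scale | 0.19 | 0.15 |

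The third row can be checked by hand. The mean log ratio is normal with mean −ln 2 and SD 0.5/√n, so the probability that it is zero or more is Φ(−ln 2 × √n / 0.5). At n=2 this is Φ(−1.96) = 0.025. At n=3 it is Φ(−2.40) = 0.008.

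**Step 2: when the sign reverses.** Let n−1 patients share one baseline and fall by a fraction h, while the top patient has R times that baseline and rises by a fraction g. The raw mean is positive when R > (n−1)h/g. With h = 0.5 and g = 0.2, R must exceed 0.5/0.2 = 2.5 at n=2 and 2 × 0.5/0.2 = 5 at n=3. If every patient falls, the sign cannot reverse.

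**Step 3: worked examples (invented values).**
- n=3, baselines 400, 800, 8000; two halve and the top one rises 20%. Changes are −200, −400, +1600. The mean is +333 and the median −200. The geometric mean ratio is (0.5 × 0.5 × 1.2)^(1/3) = 0.67.
- n=2, baselines 400 and 8000; one halves and the top one rises 20%. Changes are −200 and +1600. Mean and median are both +700. The ratio is √(0.5 × 1.2) = 0.77.
- n=2, same baselines, both halve. Changes are −200 and −4000, mean −2100. The sign is right, but 4000/4200 = 95% of the change is one patient's, and nothing in −2100 says that both levels halved.

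**Step 4: what the planned median does.** At n=3 it points the right way in the first example. At n=2 it equals the mean and gives no protection. At n=1 there is no dominance and no reversal; only the relative size is missing.

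**The case against.** The case for leaving the plan alone has real weight.

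- **Spread.** Protocol 3.2.2 reports IP-10 "serum levels, were on average over 77-fold higher than controls". A reader might take this as evidence that patients differ from one another by large multiples. It is an average elevation over controls in CANDLE and says nothing about variation between patients. The spreads used above are assumptions.
- **Sample size.** A reader might picture one mean over all 5 patients, dominated by one of them. SAP 6.8.1 summarises within disease, so no such mean is planned. This stands, and it is why the figures above are for two and three patients.
- **Existing safeguards.** SAP 6.1 requires the median, minimum and maximum, which expose an outlier at three patients. Listings are a main tool, and Protocol 10.3.3 promises listings of efficacy measures over time. This largely stands. However, the specific listings in SAP 6.8.3 and 6.12.4 do not name cytokines or hsCRP. Nor does the spaghetti-plot sentence, although its wording leaves room for them.
- **Model.** The simulation assumes multiplicative change, which favours the ratio scale by construction, and it compares two different summaries: relative change in the arithmetic mean, and a geometric mean ratio. That is a fair limit on the precision figures. It does not touch the weighting by level, which is plain arithmetic.
- **Logs have their own weakness.** With one patient unchanged and one falling 100-fold to a substituted assay limit, the geometric mean ratio is √(1 × 0.01) = 0.10, which looks like a 90% fall overall. This stands, and is the reason to show each patient's fold change too.
- **Timing.** SAP section 3 shows that the primary and 52-week locks have passed. Replacing the scale now would break comparability with those outputs. This argues for adding a summary, not replacing one.

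**Conclusion.** The point holds as a cheap improvement. Where a disease has two or three patients, the raw mean change in cytokines and hsCRP is carried mainly by one patient: a median 71% to 84% of the absolute change at n=2 and about 56% to 72% at n=3. It is also less precise than the ratio and gives no relative size. These figures rest on the assumed halving, the within-patient log SD of 0.5 and a geometric SD of 2 to 5.

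A reader might infer that the plan is likely to report the wrong direction, or that a main conclusion is at risk. The documents do not support either. A reversal needs the high-level patient to move against the others, and under these assumptions the raw mean has the right sign in about 94% to 97% of trials. The markers are exploratory, nothing is tested, and the primary endpoint is the diary score, for which a raw difference is suitable.

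**What to change.** In SAP 6.8.3, for cytokine concentrations and hsCRP, and for CRP in item 7 for consistency, add the ratio to baseline by visit and disease (geometric mean, median and range). Name these markers in the listing and plot sentences, showing fold change for each patient.

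Keep the planned raw summaries so that outputs from the earlier database locks remain comparable. Leave the IFN signature score as a difference; SAP 6.8.3 gives its formula. The SAP gives no scale for the IFN response gene score, so confirm it before choosing between a difference and a ratio. State the value to be used for results below the assay limit.

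The cost is a few lines of SAP text and a log transform in programming, with no new data. Version 5 is to be approved before the final database lock, so it could carry the change. The small downside is that results at the assay limit depend on the substituted value.

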**Table JAJE.4 Thresholds for calculating proportion of days meeting response criteria**

Variables	Disease	Threshold
daily diary score (average scores across symptoms)	NNS/CANDLE	daily score to <0.5
		daily score to <1.0
	SAVI	daily score excluding the respiratory/breathing symptom score to <1.0
		daily score to <0.5
		daily score excluding the respiratory/breathing symptom score to <0.5

	AGS	daily score to <0.5
		daily score excluding neurological symptoms to <0.5
Symptom specific daily diary score	NNS/CANDLE	daily score to 0
	SAVI	daily score to 0
	AGS	daily score to 0

Proportion of patients who result in a decrease in the daily dose of corticosteroids (systemic corticosteroids <0.15 mg/kg/day oral prednisone or a decrease of at least 50% of the patient's daily dose at baseline) by visit. Prednisone (or equivalent) for the daily dose of corticosteroids will be used for the analysis. Dose of corticosteroids taken at the visit date will be used as the representative value of the dose at the visit.

A by-visit listing of the calculated mean diary score (defined in Section 6.9.1), change in diary score, percent change in diary score, mean symptom scores, and change from baseline in each symptom score will be provided. In addition, spaghetti plot of efficacy measures including the calculated mean diary score, Physician's Global Assessment of Disease Activity score and Prednisone (or equivalent) dose of systemic corticosteroids for the primary diseases will be provided.

#### 6.8.3.1. Comparison against pre-treatment period (NNS/CANDLE only)

In order to assess the change from pre-treatment period for NNS/CANDLE patients of efficacy measurements during baricitinib treatment period, the same analyses for the following primary and secondary efficacy variables will be performed by using average of data during pre-treatment period as a baseline value.

- Mean daily diary score
- Patient's symptom specific daily diary scores
- Proportion of days which meets a threshold of response criteria (See section 6.1)
- Physician's Global Assessment of Disease Activity scores

Proportion of days which meets a threshold of response criteria during both pre-treatment period and primary treatment period will be calculated.

#### 6.8.3.2. Patient's relative retrospective medical records

This study will collect case report form data for parameters that define disease symptoms retrospectively of up to a maximum of 5 years from the point at when the patient participates in

Study JAJE (screening visit). The following data will be used for by-patient listing. Graphical presentation of change from the start of the patient's relative retrospective medical records may be shown.

- Laboratory testing (e.g. CRP, complete blood cell count, AST, ALT, gammaglutamyltransferase [GGT], creatine phosphokinase [CPK])
- Classification of disease severity (e.g. classification of disease severity for NNS patients, Barthel index)

## 6.9. Health Outcomes/Quality-of-Life Analyses

### 6.9.1. Patient Diary and Diary Score

#### 6.9.1.1. NNS/CANDLE Diary

The patient diary for NNS/CANDLE is provided for daily collection of information on patients' signs and symptoms. NNS/CANDLE patients (or caregiver) record daily symptoms of fever, rash, musculoskeletal pain, headaches, and fatigue. Each symptom is rated on a scale of 0 to 4, with 0 = no symptoms, 1 = mild symptoms, 2 = moderate symptoms, 3 = more severe symptoms, and 4 = severe symptoms (possible range of total score 0 to 20). At each visit, the average daily diary score is calculated as follows:

- Average score of each symptom is calculated using data from 7 days preceding the current visit (not including data on the day of current visit).
- The calculated average score for each symptom is summed up and divided by the number of assessed symptoms (ie, 5 symptoms for NNS/CANDLE) to calculate the average score for each patient.

#### 6.9.1.2. SAVI Diary

The patient diary for SAVI is provided for daily collection of information on patients' signs and symptoms. SAVI patients (or caregiver) record daily symptoms of fever, rash, musculoskeletal pain, fatigue, respiratory symptoms, and severity of ulcers/ischemic lesions. Each symptom is rated on a scale of 0 to 4, with 0 = no symptoms, 1 = mild symptoms, 2 = moderate symptoms, 3 = more severe symptoms, and 4 = severe symptoms (possible range of total score 0 to 24).

At each visit, the average daily diary score is calculated as follows:

- Average score of each symptom is calculated using data from 7 days preceding the current visit (not including data on the day of current visit).
- The calculated average score for each symptom is summed up and divided by the number of assessed symptoms (ie, 6 symptoms for SAVI) to calculate the average score for each patient.

- Additionally, the average diary score is calculated as the average of the symptom scores, excluding the respiratory/breathing symptom score.

#### 6.9.1.3. AGS Diary

The patient diary for AGS is provided for daily collection of information on patients' signs and symptoms. AGS patients (or caregiver) record daily symptoms of neurologic disability, crying, length of uninterrupted sleep, generalized seizure, fever, excessive irritability, skin findings (body), and skin findings (hands, feet, and ears). Each symptom is rated on a scale (possible range of total score 0 to 34). At each visit, the average daily diary score is calculated as follows:

- Average score of each symptom is calculated using data from 7 days preceding the current visit (not including data on the day of current visit).
- The calculated average score for each symptom is summed up and divided by the number of assessed symptoms (ie, 8 symptoms for AGS) to calculate the average score for each patient.
- Additionally, the average diary score is calculated as the average of the symptom scores excluding neurological symptoms.

### 6.10. Other exploratory analyses

If sample size allows, two-dimensional plots of various data may be utilized to explore the relationship between variables of interest. For example, plots of efficacy measures such as change from baseline in mean daily diary score or proportion of days meeting response criteria versus change in laboratory measures may be used to explore risk/benefit relationships.

### 6.11. Bioanalytical and Pharmacokinetic/Pharmacodynamic Methods

This will be described in a separate Pharmacokinetic Analysis Plan.

### 6.12. Safety Analyses

All safety data will be descriptively summarized by disease diagnosis for the safety population. The safety outcomes include TEAEs, TEAEs related to study drug, adverse events of special interest (AESI), serious AEs (SAEs), laboratory analytes, and vital signs.

#### 6.12.1. Extent of Exposure

A by-patient listing will be created including the visit, week, patient's weight, total daily dose, total daily dose per weight (mg/kg), dose frequency, the treatment start date or dose adjustment date, and so on.

Baricitinib exposure will be summarized based on duration of exposure to baricitinib, and the patient years of exposure (PYE). PYE is defined as the sum of all patient exposure time in years for the specific disease diagnosis. A by-patient listing of study drug exposure will be provided

including duration of exposure in years and separately in weeks. Duration in days of baricitinib exposure is defined as the date of last dose of baricitinib minus the date of first dose of baricitinib +1.

## 6.12.2. Adverse Events

Adverse events are classified based upon the Medical Dictionary for Regulatory Activities (MedDRA). Each AE will be coded to system organ class (SOC) and Preferred Term (PT) using the MedDRA version that is current at the time of database lock. Severity of AEs is recorded as mild, moderate, or severe. Adverse events will use the safety population defined in Section 6.3.

Summaries will consist of the frequency and percent of patients experiencing each AE. For summaries, SOC will be sorted in alphabetical order and PT in decreasing frequency within SOC by the total group. Patients will only be counted once, regardless of how many conditions are included under the same SOC and PT.

All AE listings will include AE type (pre-existing condition or TEAE), SOC, PT, reported term, event start and end date, start and end day, severity, related to study drug or non-study drug treatment, SAE status, reason AE is classified as serious, and event outcome.

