Maintenance Treatment Period

After completing the primary treatment period at Visit 12 for NNS/CANDLE and at Visit 15 for SAVI and AGS respectively, patients will enter the maintenance treatment period.

Each patient will continue to receive baricitinib at their optimized dosage until whichever occurs first:

- Visit 36 (Week 244) during the maintenance treatment period, **OR**
- baricitinib is commercially available for NNS/CANDLE, SAVI, and/or AGS. All patients will move to early termination visit (ETV) within 6 months after marketing authorization of baricitinib.

Patients should maintain their optimized dosage during the maintenance treatment period as much as possible. If dose modification is conducted, the investigator must notify Lilly or its designee as soon as possible.

Post-Treatment Follow-Up Period

Patients discontinuing from study treatment who have received at least 1 dose of baricitinib will continue to the early termination visit. Patients who discontinue study treatment, or who complete the study treatment, will have a posttreatment follow-up visit (Visit 801) approximately 28 days after the last dose of baricitinib. As an exception, patients who will transition from this study to commercial baricitinib are not required to have Visit 801. Other therapy for NNS/CANDLE, SAVI, or AGS, as determined to be appropriate by the investigator, is allowed during the post-treatment follow-up period.

Number of Patients

Because the medical conditions being treated in the study are very rare in Japan, it is anticipated that relatively few patients will be enrolled. Approximately 5 patients will be enrolled. The Sponsor will try to enroll more than 1 patient per disease.

However, given the scarcity of patient population for each of these target diseases in Japan, it may be possible that the study is completed without enrolling any patients for a specific disease if no eligible patients could be found.

Statistical Analysis

Because the medical conditions being treated in this study are rare, it is anticipated that relatively few patients will be enrolled. Therefore, no formal statistical analyses are planned. Instead, descriptive summaries, where applicable, and data listings will be the main tools used to summarize the results from this study.

2. Schedule of Activities

Table JAJE.1. Schedule of Activities (Screening Period and Pretreatment Period)

	NNS/CANDLE		SAVI and AGS	
	Screening	Pretreatment	Screening	Pretreatment
Visit #	1	1A	2	3

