10.1. Sample Size Determination

Because the medical conditions being treated in the study are very rare in Japan, it is anticipated that relatively few patients will be enrolled. Approximately 5 patients will be enrolled. The Sponsor will try to enroll more than 1 patient per disease.

However, given the scarcity of patient population for each of these target diseases in Japan, it may be possible that the study is completed without enrolling any patients for a specific disease if no eligible patients could be found.

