10.3.4. Safety Analyses

Safety measures will be summarized and/or listed. Standard listings will include TEAEs, SAEs, and results from laboratory tests. By definition, TEAEs are AEs that begin or increase in severity after the patient receives the first dose of baricitinib. Summaries of the incidence and event counts of TEAEs and SAEs, of abnormal shifts in laboratory values, or of per-visit distributions of laboratory results will be created. Other data, including body weight and height data will be reported in patient listing. Weight, height, occipital frontal circumference measurement (children less than 3 years old), and body mass index data will be merged to the Japanese children standard growth data issued by the Japanese Association for Human Auxology to compare subjects' growth with the standard (Isojima et al. 2016).

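### The SAP's clinical AE summaries count patients only, omitting the event counts the protocol plans for TEAEs and SAEs and any use of patient-years as an AE denominator

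*SAP*

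**What the plan says.** Protocol 10.3.4 names, among the safety outputs, "Summaries of the incidence and event counts of TEAEs and SAEs".

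SAP 6.12.2 sets a single metric: "Summaries will consist of the frequency and percent of patients experiencing each AE". It adds the counting rule "Patients will only be counted once, regardless of how many conditions are included under the same SOC and PT". SAP 6.12.2.3 then has TEAEs summarized by SOC and PT. SAEs enter the overview in 6.12.2.1 and a by-patient listing in 6.12.2.2. AESIs, which include every preferred term in the infections SOC, get a by-patient listing in 6.12.3.1.

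On exposure, SAP 6.12.1 states "PYE is defined as the sum of all patient exposure time in years for the specific disease diagnosis" and reports PYE as an exposure summary. No AE analysis in 6.12.2 or 6.12.3 divides by it.

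Protocol 10.1 gives the size: "Approximately 5 patients will be enrolled", spread over three diseases, and SAP 6.12 presents safety by disease. The synopsis sets the upper limit of treatment at "Visit 36 (Week 244) during the maintenance treatment period", unless baricitinib first becomes commercially available. In that case "All patients will move to early termination visit (ETV) within 6 months after marketing authorization of baricitinib".

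Event counts do occur once in the SAP. Section 6.18 provides them for each serious and other AE term in the registry dataset.

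**The concern.** The protocol plans two measures and the SAP's clinical summaries carry one. The SAP revision history records no decision to leave event counts out, so this looks like an omission.

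The missing measure matters in this design for three reasons:

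- **Recurrence.** Protocol 3.2 says the commonest TEAEs in rheumatoid arthritis patients fall in the infections SOC, and infections can recur. A patient with one infection and a patient with fifteen make the same SOC entry.
- **Coarseness.** With one patient in a disease column the percentage can only be 0 or 100. With two it can only be 0, 50 or 100. Event counts and time at risk carry most of the remaining information.
- **Follow-up time.** Treatment may end at Week 244, at early stopping, or on marketing authorization. Data are analyzed after the primary treatment period, after Week 52 (SAP 6.15) and at final lock. A cumulative percentage of patients grows between these cuts even if risk is constant.

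At stake is how the study's safety tables are read: a rising percentage could be taken for rising risk, and a heavy burden of repeated events could look the same as a light one.

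**Working it through.** The documents state no AE rate or AE percentage, so there is no plan figure to reproduce. The check asks how a percentage of patients behaves over this follow-up.

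**Inputs from the documents.** About 5 patients (Protocol 10.1). Maximum treatment to Week 244 (Protocol synopsis and 5.1). Analyses after the primary treatment period, which ends at Week 32 for SAVI and AGS, and after Week 52 (SAP 6.15).

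**Assumption.** Events follow a constant Poisson rate r per patient-year. The documents do not give r, so a range is shown.

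**Follow-up time.** T = weeks × 7 / 365.25:

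- Week 32: 224 / 365.25 = 0.61 years
- Week 52: 364 / 365.25 = 1.00 year
- Week 244: 1708 / 365.25 = 4.68 years

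**Expected percent of patients with at least one event.** P = 1 − exp(−rT):

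| r per patient-year | Week 32 | Week 52 | Week 244 |
|---|---|---|---|
| 0.02 | 1% | 2% | 9% |
| 0.05 | 3% | 5% | 21% |
| 0.1 | 6% | 10% | 37% |
| 0.2 | 12% | 18% | 61% |
| 0.5 | 26% | 39% | 90% |
| 1 | 46% | 63% | 99% |
| 2 | 71% | 86% | about 100% |

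At r = 0.5, for example, Week 244 gives 1 − exp(−0.5 × 4.68) = 0.90. The rise along each row is due to time alone.

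**Rate needed to approach 100%.** For 95% affected by Week 244, r = −ln(0.05) / 4.68 = 0.64 per patient-year. The chance that all 5 patients are affected is P⁵ by Week 244: 0.7% at r = 0.1, 8% at 0.2, 60% at 0.5 and 95% at 1.

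**What event counts and PYE would add.** Maximum exposure is 5 × 4.68 = 23.4 patient-years. Three outcomes that would each read 5/5 (100%) separate as follows:

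- 5 events: 5 / 23.4 = 0.21 per patient-year (21 per 100 PYE)
- 25 events: 25 / 23.4 = 1.07 (107 per 100 PYE)
- 70 events: 70 / 23.4 = 2.99 (299 per 100 PYE)

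**The case against.** The strongest reply is that nothing is lost. Both documents make listings a main tool. SAP 6.12.2 and 6.12.2.1 list every AE by patient with start and end dates, 6.12.2.2 lists SAEs, 6.12.3.1 lists AESIs by category, and 6.12.1 lists each patient's exposure. With about 5 patients a reader can see each recurrence directly. Registry output under 6.18 also gives event counts per term, and its optional 5% threshold would remove nothing, since 1 of 5 patients is already 20%. The protocol wording is loose as well: 10.3.4 allows safety measures to be summarized, listed or both, and its sentence on summaries offers alternatives. SAP 6.1 lets lesser departures from protocol methods be explained in the CSR.

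Much of this stands. A reader might infer that event counts have vanished, that PYE goes unused, or that the plan cannot show event burden. The documents do not support any of these: counts survive in 6.18, PYE is reported as exposure, and the dated listings show burden patient by patient.

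It does not remove the gap. The protocol names event counts as a summary, and hand counting from listings is not one. The registry output is by preferred term and treatment group, not by SOC or disease. It includes SAEs whether or not they are treatment-emergent, and has no exposure denominator.

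A request for exposure-adjusted rates goes beyond the protocol, which promises none. It is a recommendation. Exact Poisson intervals would be a poor addition: with perhaps 1 to 3 patients per disease, repeated events cluster within patients, so intervals assuming independence would be too narrow, and the plan is deliberately descriptive.

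**Conclusion.** The point holds as a gap between protocol and SAP in the clinical AE summaries, worth correcting but not a threat to the trial. SAP 6.12.2 leaves out the event counts that Protocol 10.3.4 plans, and no AE analysis in the SAP uses PYE as a denominator.

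The size depends on rates that the documents do not give. Under a constant 0.5 events per patient-year, the expected percentage of patients affected moves from 26% to 90% between Week 32 and Week 244 with no change in risk.

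A reader might go further and expect AE percentages to reach 100% across the board. That does not follow. Near-saturation needs about 0.6 events per patient-year or more over the full 244 weeks, which may suit any-TEAE or a common SOC. Rare preferred terms, and SAEs or AESIs with low rates, would stay well below: 9% at 0.02 and 37% at 0.1 per patient-year. Week 244 is also a maximum. At the earlier analyses even a rate of 1 per patient-year gives only 46% (Week 32) or 63% (Week 52).

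**What to change.** In SAP 6.12.2 and 6.12.3, before the final database lock:

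1. Add the number of events beside n (%) for TEAEs by SOC and PT, for SAEs and for infection AESIs, by disease and overall. This restores the protocol's event counts.
2. Beside it, show descriptive events per 100 PYE, using the PYE from 6.12.1 by disease and its sum overall. Give no Poisson intervals.
3. Keep the once-per-patient rule for n (%), and state that it does not apply to the event column.

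The data are already collected, so the cost is a few extra columns and a short summary for SAEs and infection AESIs where only listings are specified. The downside is that one patient with many events can dominate a rate. The tables should say so and direct the reader to the by-patient listings.
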